8.2.3. Electronic Diary

Participants will be required to complete a reactogenicity e-diary through an application installed on a provisioned device or on the participant's own personal device. All participants will be asked to monitor and record local reactions, systemic events, and use of antipyretic medication for 7 days from the day of administration of the study intervention. The reactogenicity e-diary allows the recording of these assessments only within a fixed time window, thus providing the accurate representation of the participant's experience at that time. Data on local reactions and systemic events reported in the reactogenicity e-diary will be transferred electronically to a third-party vendor, where they will be available for review by investigators and the Pfizer clinicians at all times via an internet-based portal.

At intervals agreed to by the vendor and Pfizer, these data will be transferred electronically into Pfizer's database for analysis and reporting. These data do not need to be reported by the investigator in the CRF as AEs if reported in the e-diary.

Investigators (or designee) will be required to review the reactogenicity e-diary data online at frequent intervals as part of the ongoing safety review.

The investigator or designee must obtain stop dates from the participant for any ongoing local reactions, systemic events, or use of antipyretic medication on the last day that the reactogenicity e-diary was completed. The stop dates should be documented in the source documents and the information entered in the CRF.

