- The investigator or appropriately qualified designee reviews the reactogenicity e-diary data online following vaccination to evaluate participant compliance and as part of the ongoing safety review. Daily review is optimal during the active diary period.

8.9.2. Visit 2 – Vaccination 2 – 28 to 42 Days After Visit 1

- Record AEs as described in [Section 8.3](#).
- Ensure and document that the participant continues to be eligible for the study (see [Section 7](#) for participant discontinuation/withdrawal) and that none of the temporary delay criteria are met.
- Record nonstudy vaccinations as described in [Section 6.8](#).
- Record prohibited medication as described in [Section 6.8.1](#).
- Perform urine pregnancy test on WOCBP as described in [Section 8.2.5](#).
- Discuss contraceptive use as described in [Section 5.3.1](#).
- Review the participant's e-diary data. Collect stop dates of any e-diary events (local reactions or systemic events) ongoing on the last day that the reactogenicity e-diary was completed and record stop dates in the CRF.
- Measure and record the participant's oral temperature (°C).
- Obtain the participant's study intervention container allocation using the IRT system.
- Collect a blood sample of approximately 30 mL for immunogenicity assessments prior to vaccination.
- An unblinded site staff member will administer a single 0.3-mL injection of the BNT162b2 or saline into the left deltoid muscle.
- Blinded site staff will observe the participant for at least 30 minutes after administration of the BNT162b2 or saline for any reactions. Record any AEs on the CRF and on the Vaccine SAE Reporting Form, as applicable.
- Confirm that the e-diary is working and review instructions, if necessary. Ask the participant to complete the reactogenicity e-diary from Day 1 through Day 7, with Day 1 being the day of vaccination. Provide thermometer or measuring device, if needed.

- Ask the participant to contact the site staff or investigator immediately if the participant experiences any of the following from Day 1 through Day 7 after vaccination (where Day 1 is the day of vaccination) to determine if an unscheduled reactogenicity visit is required:
 - Fever $\geq 39.0^{\circ}\text{C}$ ($\geq 102.1^{\circ}\text{F}$).
 - Redness or swelling at the BNT162b2 or saline injection site measuring greater than 10 cm (>20 measuring device units).
 - Severe pain at the BNT162b2 or saline injection site.
 - Any severe systemic event.

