Swelling	>2.0 cm to 5.0 cm (5 to 10 measuring device units)	>5.0 cm to 10.0 cm (11 to 20 measuring device units)	>10 cm (≥21 measuring device units)	Necrosis

- a. Only an investigator or qualified designee is able to classify a participant’s local reaction as Grade 4, after clinical evaluation of the participant or documentation from another medically qualified source (eg, emergency room or hospital record). Grade 4 local reactions will be collected on the AE case report form and assessed by the investigator using the AE intensity grading scale.

If a Grade 3 local reaction is reported in the reactogenicity e-diary, a telephone contact should occur to ascertain further details and determine whether a site visit is clinically indicated. Only an investigator or medically qualified person is able to classify a participant's local reaction as Grade 4. If a participant experiences a confirmed Grade 4 local reaction, the investigator must immediately notify the sponsor and, if it is determined to be related to the administration of the study intervention, further vaccinations will be discontinued in that participant.

For each local reaction after each vaccination, the maximum severity grade will be derived for the e-diary collection period (within 7 days after each vaccination) as follows:

Maximum severity grade = highest grade (maximum severity) within 7 days after vaccination among the severity grades reported for that local reaction in the e-diary.

Duration (First to Last Day Reported)

The duration (days) of each local reaction will be calculated as the number of days from the start of the first reported reaction to the resolution of the last reported reaction, inclusive. Resolution is defined as the last day on which the reaction is recorded in the e-diary if the reaction lasts 7 days or less, or the day the reaction ends if it persists beyond the end of the reactogenicity e-diary period following vaccination (the latter will be collected on the CRF). If there is no known date when the reaction ended, then duration will be missing (unknown). However, if a reaction is ongoing at the time of a subsequent vaccination, the end date/day for the ongoing event would be the date/day that the next vaccination is administered, which will be used for the duration computation. Participants with no reported reaction have no duration.

Onset Day

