3.1.1.2. Systemic Events (Systemic Event Symptoms and Fever)

The systemic events assessed and recorded in the e-diary are fever, fatigue/tiredness, headache, chills, vomiting, diarrhea, new or worsened muscle pain, and new or worsened joint pain within 7 days after each vaccination. The derivations for systemic events will be handled similarly to the way local reactions are handled for presence of event, severity level, duration, and onset day (see [Section 3.1.1.1](#)).

The systemic events will be assessed by the participant as mild, moderate, or severe according to the grading scale in [Table 5](#).

If a Grade 3 systemic event is reported in the reactogenicity e-diary, a telephone contact should occur to ascertain further details and determine whether a site visit is clinically indicated. Only an investigator or medically qualified person is able to classify a participant's systemic event as Grade 4. If a participant experiences a confirmed Grade 4 systemic event, the investigator must immediately notify the sponsor and, if it is determined to be related to the administration of the study intervention, further vaccinations will be discontinued in that participant.

Table 5. System Event Grading Scale

Systemic Event	Mild (Grade 1)	Moderate (Grade 2)	Severe (Grade 3)	Potentially Life Threatening (Grade 4) ^a
Vomiting	1 to 2 times in 24 hours	>2 times in 24 hours	Requires IV hydration	Emergency room visit or hospitalization for hypotensive shock
Diarrhea	2 to 3 loose stools in 24 hours	4 to 5 loose stools in 24 hours	6 or more loose stools in 24 hours	Emergency room visit or hospitalization for severe diarrhea
Headache	Does not interfere with activity	Some interference with activity	Prevents daily routine activity	Emergency room visit or hospitalization for severe headache
Fatigue/tiredness	Does not interfere with activity	Some interference with activity	Prevents daily routine activity	Emergency room visit or hospitalization for severe fatigue
Chills	Does not interfere with activity	Some interference with activity	Prevents daily routine activity	Emergency room visit or hospitalization for severe chills
New or worsened muscle pain	Does not interfere with activity	Some interference with activity	Prevents daily routine activity	Emergency room visit or hospitalization for severe new or worsened muscle pain

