6.1.1.1.2. Supplemental Analyses

To support the assessment of local reactions, the following endpoints (as defined in [Section 3.1.1.1](#)) will be summarized with the same analysis time point and analysis population as above, and appropriate analysis methodology and reporting results. Confirmed e-diary errors will be excluded from these analyses.

- Duration (days) of each local reaction after each vaccination.
- Onset day of each local reaction after each vaccination.

These continuous endpoints will be summarized by displaying n, mean, median, standard deviation, minimum, and maximum for each vaccination, by vaccine group.

Figures:

Bar charts with the proportions of participants for each local reaction throughout 7 days after each vaccination will be plotted for each vaccination, by vaccine group. The bars will be divided into severity categories to highlight the proportions of participants by maximum severity.

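### For reactions of 7 days or less, the SAP takes the last e-diary entry as the end, so an early-stopped diary cuts the duration short although the protocol collects a CRF stop date.

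*SAP*

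**What the plan says.** SAP 3.1.1.1 defines duration as "calculated as the number of days from the start of the first reported reaction to the resolution of the last reported reaction, inclusive". Resolution then has two branches.

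- Branch 1: "Resolution is defined as the last day on which the reaction is recorded in the e-diary if the reaction lasts 7 days or less".
- Branch 2: "or the day the reaction ends if it persists beyond the end of the reactogenicity e-diary period following vaccination", with that day taken from the CRF.

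Two further rules follow. Duration is missing if the end date is unknown, and a reaction still present at the next vaccination is ended on that vaccination date.

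The protocol fixes the diary period at Day 1 through Day 7 (8.9.1 and 8.9.2). Its trigger for collecting a stop date is different from the SAP's. Under 8.2.3 the site "must obtain stop dates from the participant for any ongoing local reactions, systemic events, or use of antipyretic medication on the last day" of diary completion, and the date goes into the CRF. The Visit 2 procedures in 8.9.2 repeat this for events "ongoing on the last day that the reactogenicity e-diary was completed and record stop dates in the CRF". Visit 3 (8.9.3) has the same trigger, with CRF entry if required. Protocol 8.2.3.2, on local reactions, instead uses the SAP's branch 2 trigger, persistence past the end of the diary period.

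On late entry, protocol 8.2.3 says: "The reactogenicity e-diary allows the recording of these assessments only within a fixed time window". On systemic events, SAP 3.1.1.2 says: "The derivations for systemic events will be handled similarly to the way local reactions are handled". SAP 3.1.1.3 applies the local-reaction rules to antipyretic use where applicable.

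**The concern.** The last completed diary day need not be Day 7. A participant can stop making entries on Day 3 with pain still present, and the missed days cannot be filled in afterwards. Such a diary stays in the analysis: under SAP 3.4.2 any data on any day counts as transmitted, and SAP 6.1.1.1.1 drops only participants with no diary data at all for that vaccination.

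For such a participant the last entry shows that the reaction had not yet ended. It is a censoring time. Branch 1 treats it as the end, although the protocol has asked for the end date and recorded it.

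At stake is a planned supporting summary, "Duration (days) of each local reaction after each vaccination", and its counterpart for systemic events in SAP 6.1.1.2.2, reported as n, mean, median, standard deviation, minimum and maximum by vaccine group.

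**Working it through.** The plan states no figure for duration, so there is nothing to reproduce. The check applies the SAP rule to individual records and then illustrates an average.

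**Single records.** Let o be the onset day, L the last diary day with the reaction present, and E the stop day reported on the CRF. Duration is end day − o + 1. Branch 1 (E − o + 1 ≤ 7) uses L as the end. Branch 2 (E > 7) uses E.

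| o | L | E | Branch 1 | Branch 2 | Using the CRF stop date |
|---|---|---|---|---|---|
| 1 | 3 | 6 | 3 − 1 + 1 = 3 | does not apply | 6 |
| 1 | 3 | 9 | does not apply (9 days) | 9 | 9 |
| 1 | 1 | 7 | 1 | does not apply | 7 |
| 4 | 7 (complete diary) | 9 | 7 − 4 + 1 = 4 | 9 − 4 + 1 = 6 | 6 |
| 4 | 5 | 9 | 2 | 6 | 6 |

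Rows 1 and 2 have identical diaries. Moving the reported stop by three days, from Day 6 to Day 9, triples the derived duration.

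Rows 4 and 5 show a second defect. A reaction that starts late can last 7 days or less and still run past Day 7. Both branches then apply and give different answers, even with a complete diary.

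**All early-stop cases ending by Day 7.** The combinations with o ≤ L < E ≤ 7 number C(8,3) = 56. In every one only branch 1 applies, and the duration falls short of the CRF-based value by E − L, which is 1 to 6 days.

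**Other SAP rules.** The unknown-end rule does not help when a CRF date exists, because the end is known. The next-vaccination rule does not reach these cases, because Vaccination 2 is 28 to 42 days later.

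**Illustrative average.** The documents give neither a diary-completion rate nor a duration distribution, so every input here is an assumption:

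- onset on Day 1 (70%) or Day 2 (30%);
- geometric duration with mean m = 2, 3 or 4 days;
- permanent diary stop with daily probability h = 1%, 2%, 5% or 10%, so that (1 − h)^6 of diaries reach Day 7 (94% at h = 1%, 74% at 5%, 53% at 10%);
- the CRF stop date is taken as exact.

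Over the 12 scenarios:

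- 0.9% to about 14% of reported reactions are shortened, by 1.8 to 2.3 days each on average.
- Mean duration is understated by 0.8% to 9.2%.
- At h = 5% and m = 3, 6.7% are shortened by 2.14 days on average, so the mean is 3.00 − 0.067 × 2.14 = 2.86 days (−4.8%).
- At h = 1% to 2% the mean moves by 0.02 to 0.07 days.
- The median is unchanged in 11 of the 12 scenarios.

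**The case against.** The SAP labels the measure as running from first to last day reported, and the protocol prefers time-locked entries because they capture the experience when it happens. Scheduled collection of stop dates is at Visits 2 and 3, four to six weeks after the vaccination, so these dates may rest on recall. Protocol 8.2.3.2 uses the same trigger as branch 2, so the SAP follows one of two protocol formulations. Part of this stands: the CRF date is a reported date, not a known true one, and the mismatch begins inside the protocol. It does not rescue branch 1. The SAP already relies on CRF stop dates for longer reactions, where recall is no better, so recall gives no reason to discard the same item for shorter ones.

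The diary period might also be read as ending on the participant's own last completed day. The protocol fixes it at Day 1 through Day 7, and branch 1 would still apply to a reaction of 7 days or less.

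Three stronger readings are tempting, and the documents do not support them:

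- *A reaction with no stop date gets a falsely short duration.* Without an end date, nobody can establish that the reaction lasted 7 days or less, and the SAP's own rule makes the duration missing.
- *Durations after coadministration in particular are understated.* The rule is identical in both groups and after both vaccinations, and nothing in the documents points to a differential effect.
- *The percentages above estimate the effect in this trial.* They rest wholly on assumed stop rates. The upper end needs almost half of diaries to stop before Day 7, while the protocol describes daily site review of diary data as optimal.

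**Conclusion.** The point holds as a minor defect in a derivation rule. For a reaction that ends by Day 7 after the diary has stopped early, the SAP as written does not use the stop date the protocol requires and shortens the duration by 1 to 6 days relative to it. Reactions lasting more than 7 days and ending after Day 7 are handled correctly. Late-onset reactions of 7 days or less that run past Day 7 fall under both branches, so their duration is ambiguous.

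That the shortening goes in one direction depends on taking the reported stop date as the reference. Its average size cannot be computed from the documents; about 0.8% to 9% of mean duration is illustrative, and with few early stops it is close to nil. Only the supplemental duration summaries in SAP 6.1.1.1.2 and 6.1.1.2.2 are affected. Presence, maximum severity, the primary safety percentages and the noninferiority tests do not use duration.

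**What to change.** Replace the resolution sentence in SAP 3.1.1.1 with wording such as:

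> If the reaction was not ongoing on the last day the participant completed the e-diary, resolution is the latest diary day on which it was entered. If it was ongoing on that day, whether Day 7 or earlier, resolution is the stop date reported on the CRF.

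Keep the existing rules for an unknown end date and for a reaction ongoing at the next vaccination. Apply the same wording to systemic events and, where applicable, antipyretic use. This also removes the overlap between the branches: onset Day 4 with a reported end on Day 9 then gives 6 days. Aligning the trigger in protocol 8.2.3.2 with 8.2.3 would remove the source of the mismatch.

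The cost is one SAP sentence and one condition in the diary programming; protocol 8.2.3 already requires the stop dates. The downside is that some end dates within the 7-day window will rest on participant recall, as they already do for longer reactions.

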3.1.1.2. Systemic Events (Systemic Event Symptoms and Fever)

The systemic events assessed and recorded in the e-diary are fever, fatigue/tiredness, headache, chills, vomiting, diarrhea, new or worsened muscle pain, and new or worsened joint pain within 7 days after each vaccination. The derivations for systemic events will be handled similarly to the way local reactions are handled for presence of event, severity level, duration, and onset day (see [Section 3.1.1.1](#)).

The systemic events will be assessed by the participant as mild, moderate, or severe according to the grading scale in [Table 5](#).

If a Grade 3 systemic event is reported in the reactogenicity e-diary, a telephone contact should occur to ascertain further details and determine whether a site visit is clinically indicated. Only an investigator or medically qualified person is able to classify a participant's systemic event as Grade 4. If a participant experiences a confirmed Grade 4 systemic event, the investigator must immediately notify the sponsor and, if it is determined to be related to the administration of the study intervention, further vaccinations will be discontinued in that participant.

Table 5. System Event Grading Scale

Systemic Event	Mild (Grade 1)	Moderate (Grade 2)	Severe (Grade 3)	Potentially Life Threatening (Grade 4) ^a
Vomiting	1 to 2 times in 24 hours	>2 times in 24 hours	Requires IV hydration	Emergency room visit or hospitalization for hypotensive shock
Diarrhea	2 to 3 loose stools in 24 hours	4 to 5 loose stools in 24 hours	6 or more loose stools in 24 hours	Emergency room visit or hospitalization for severe diarrhea
Headache	Does not interfere with activity	Some interference with activity	Prevents daily routine activity	Emergency room visit or hospitalization for severe headache
Fatigue/tiredness	Does not interfere with activity	Some interference with activity	Prevents daily routine activity	Emergency room visit or hospitalization for severe fatigue
Chills	Does not interfere with activity	Some interference with activity	Prevents daily routine activity	Emergency room visit or hospitalization for severe chills
New or worsened muscle pain	Does not interfere with activity	Some interference with activity	Prevents daily routine activity	Emergency room visit or hospitalization for severe new or worsened muscle pain
New or worsened joint pain	Does not interfere with activity	Some interference with activity	Prevents daily routine activity	Emergency room visit or hospitalization for severe new or worsened joint pain

Abbreviation: IV = intravenous.

- a. Only an investigator or qualified designee is able to classify a participant's systemic event as Grade 4, after clinical evaluation of the participant or documentation from another medically qualified source (eg, emergency room or hospital record). Grade 4 systemic events will be collected on the AE case report form and assessed by the investigator using the AE intensity grading scale.

Oral temperature will be collected in the reactogenicity e-diary in the evening daily during the reactogenicity e-diary reporting period (7 days after each vaccination) and at any time during the 7 days that fever is suspected. Fever is defined as an oral temperature of $\geq 38.0^{\circ}\text{C}$ ($\geq 100.4^{\circ}\text{F}$). The highest temperature for each day will be recorded in the e-diary.

Temperatures will be measured in degrees Celsius and recorded to 1 decimal place and will be categorized according to the scale shown in [Table 6](#) during analysis.

If a fever of $\geq 39.0^{\circ}\text{C}$ ($\geq 102.1^{\circ}\text{F}$) is reported in the reactogenicity e-diary, a telephone contact should occur to ascertain further details and determine whether a site visit is clinically indicated. Only an investigator or medically qualified person is able to confirm a participant's fever as $>40.0^{\circ}\text{C}$ ($>104.0^{\circ}\text{F}$). If a participant experiences a confirmed fever $>40.0^{\circ}\text{C}$ ($>104.0^{\circ}\text{F}$), the investigator must immediately notify the sponsor and, if it is determined to be related to the administration of the study intervention, further vaccinations will be discontinued in that participant.

Table 6. Scale for Fever

$\geq 38.0\text{--}38.4^{\circ}\text{C}$ (100.4 to 101.1°F)
$>38.4\text{--}38.9^{\circ}\text{C}$ (101.2 to 102.0°F)
$>38.9\text{--}40.0^{\circ}\text{C}$ (102.1 to 104.0°F)
$>40.0^{\circ}\text{C}$ ($>104.0^{\circ}\text{F}$)

3.1.1.3. Use of Antipyretic Medication

The use of antipyretic medication to treat symptoms associated with study intervention administration will be recorded in the reactogenicity e-diary daily during the reporting period (7 days after each vaccination). For the use of antipyretic medication within 7 days after each vaccination, the following endpoints and variables will be derived for analysis following the same rules as for local reactions (see [Section 3.1.1.1](#)), where applicable.

- Presence (yes or no) of use of antipyretic medication on each day (7 days after each vaccination).
- Presence (yes or no) of use of antipyretic medication on any day (within 7 days after each vaccination).
- Duration (first to last day reported) of use of antipyretic medication.
- Onset day of use of antipyretic medication.

The use of antipyretic medication will be summarized and included in the systemic event summary tables but will not be considered a systemic event.

